6.8.4. Vital Signs

Vital sign data will be listed.

6.8.5. Electrocardiograms

Single ECG assessment will be performed at Screening visit and triplicate ECGs are required at all other assessments. ECG assessments reported by the site will include QT, PR, QRS, heart rate and QTcF. A mean score is calculated and reported for any replicate measurements having the same nominal visit. All summary statistics, analyses and figures will be based on the triplicate averaged data, except at screening. Any data obtained from ECGs repeated for safety reasons after the nominal time-points will not be averaged along with the preceding triplicates.

ECG summaries will include all ECG assessments from the on-treatment period. RR will be derived from HR. Fridericia's correction (QTcF) will be programmatically derived from QT and HR using the following formula:

$$QTcF(msec) = QT(msec) / \sqrt[3]{RR(sec)}$$

QTcF will be summarized by maximum on-treatment values using the following categories:

- <450 msec;
- ≥450 msec but ≤480 msec;
- >480 msec but ≤500 msec;
- >500 msec.

Unscheduled assessments will be utilized in addition to planned assessments. Shift tables will be provided for baseline QTcF value versus worst on-treatment value. Additionally, maximum increases from baseline (including scheduled and unscheduled assessments) will be summarized based on the following categories:

- Change >60 msec;
- Change >30 msec but ≤60 msec;
- Change ≤30 msec.

Data listings will contain the means from a triplicate as well as the parameters from each of the 3 ECGs. Note that using the mean value may result in a participant having a measurement that is not represented by an actual ECG.

7. INTERIM ANALYSES

7.1. Introduction

There are interim safety assessments and an interim analysis for futility planned on this study.

An internal safety review team will review cumulative safety and tolerability data on an ongoing basis for the interim safety assessments and document all decisions in the study TMF.

An interim analysis for futility will be performed on the first 30 participants enrolled and treated in Part 1 to assess the safety of elranatamab in terms of CRS rate using a dose regimen with 2 step-up priming doses. The primary endpoint of Grade ≥2 CRS rate during Cycle 1 will be evaluated at this analysis by the internal core study team and the decisions will be documented in the study TMF. Additional interim analyses may also be performed at other time points for the purpose of safety assessment and/or supporting clinical development.

7.2. Interim Analyses and Summaries

7.2.1. Interim Safety Assessments

An internal safety review team will review cumulative safety data during the study conduct. In addition, the incidence of the following events will each be monitored by the Sponsor throughout the study. The review results and decisions will be documented in the study TMF.

- Grade 3-4 CRS;
- Grade 3-4 ICANS;
- Grade 4 treatment-related non-hematologic events (excluding CRS and ICANS);
- Grade 3-4 treatment-related GBS/GB-like AEs;
- Grade 4 treatment-related sensory neuropathy/other IR neurologic AEs (excluding ICANS);
- Grade 3-4 treatment-related motor neuropathy;

- Grade 5 events.

If the number of participants observed to have such identified events exceeds a prespecified threshold, the study will be placed on a temporary enrollment hold by the Sponsor. During any temporary enrollment hold, no new participants can be enrolled, nor can any newly enrolled participants start study intervention. Participants who have already started study intervention may continue treatment only if the benefit/risk assessment for the participant is judged to be positive by the investigator in consultation with the sponsor.

The criteria for placing the study on temporary hold for the following safety reasons are based on Bayesian posterior probabilities. Using a non-informative Beta (0.5, 0.5) prior distribution, if the number of participants observed to have Grade 3 or 4 CRS results in a ≥ 0.80 posterior probability that the true Grade 3 or 4 CRS rate exceeds 20%, the study will be put on a temporary hold. Separate but similar criteria will be used for participants with Grade 3-4 ICANS and treatment-related Grade 4 non-hematologic events (excluding CRS and ICANS). Table 7 summarizes the minimum number of participants with such identified events that would meet the above criteria.

Table 7. Minimum Number of Participants With Identified Events That Would Prompt Temporary Enrollment Hold (CRS, ICANS, Non-hematologic treatment-related AEs)

Number of Evaluable Participants	10-13	14-18	19-22	23-36	27-30	31-35	36-39
Minimum number of participants with Grade 3-4 CRS events that would lead to a temporary enrollment hold	4	5	6	7	8	9	10
Minimum number of participants with Grade 3-4 ICANS events that would lead to a temporary enrollment hold	4	5	6	7	8	9	10
Minimum number of participants with Grade 4 treatment-related non-hematologic events (excluding CRS and ICANS) that would lead to a temporary enrollment hold	4	5	6	7	8	9	10

Prior distribution: Beta (0.5,0.5).

Criteria for 40 or more evaluable participants will be calculated such that the study will be put on temporary hold if the posterior probability that the true event rate exceeds 20% is greater than or equal to 0.80.

Evaluable participants are defined as those who have received at least 1 dose of study treatment having an identified event or those without such an event who have been followed for at least 28 days from first dose.

* The study will be put on temporary hold as soon as the minimum number of evaluable participants with the identified AEs has reached the threshold (eg, if there are 4 participants experiencing the identified AEs out of the first 6 evaluable participants, the study will be put on hold). A minimum of 4 events are required to trigger a temporary hold.

The criteria for placing the study on temporary hold for the following safety reasons are based on Bayesian posterior probabilities using a non-informative Beta (0.5, 0.5) prior distribution. Specifically,

- If the number of evaluable participants observed to have treatment-related Grade 3-4 GBS/GB-like AEs results in a posterior probability that the true rate of such events exceeding 3% is ≥ 0.80 , the study will be put on a temporary hold;
- If the number of evaluable participants observed to have treatment-related Grade 4 sensory neuropathy/other IR neurologic AEs (excluding ICANS) or treatment-related Grade 3-4 motor neuropathy results in a posterior probability that the true rate of such events exceeding 10% is ≥ 0.80 , the study will be put on a temporary hold.

Table 8 summarizes the minimum number of evaluable participants with such identified events that would meet the above criteria.

Table 8. Minimum Number of Participants With Identified Treatment-Related Events That Would Prompt Temporary Enrollment Hold (GBS/GB-like AEs, Peripheral Neuropathy/IR Neurologic AEs)

Number of Evaluable Participants	20-39	40-64	65-90	-	-	-	-	-	-
Minimum number of participants with Grade 3-4 treatment-related GBS/GB-like events that would lead to a temporary enrollment hold*	2	3	4	-	-	-	-	-	-
Number of Evaluable Participants	6-11	12-19	20-27	28-35	36-43	44-52	53-60	61-69	70-78
Minimum number of participants with Grade 4 treatment-related sensory neuropathy/IR neurologic AE (excluding ICANS) or Grade 3-4 treatment-related motor neuropathy events that would lead to a temporary enrollment hold**	2	3	4	5	6	7	8	9	10

Prior distribution: Beta (0.5,0.5).

Evaluable participants are defined as those who have received at least 1 dose of study treatment having an identified event or those without such an event who have been followed for at least 28 days from first dose.

* The study will be put on temporary hold as soon as the minimum number of evaluable participants with the identified AEs has reached the threshold (eg, for GBS/GB-like AEs, if there are 2 participants experiencing the identified AE out of the first 10 evaluable participants, the study will be put on hold). A minimum of 2 events are required to trigger a temporary hold.

** The study will be put on temporary hold as soon as the minimum number of evaluable participants with the identified AEs has reached the threshold (eg, if there are 2 participants experiencing the identified AEs out of the first 4 evaluable participants, the study will be put on hold). A minimum of 2 events are required to trigger a temporary hold.

In addition, the study will be put on temporary hold if any of the following criteria are met:

- 1 Grade 5 event of CRS (by ASTCT criteria);
- 1 Grade 5 event of ICANS (by ASTCT criteria);

- 1 Grade 5 treatment-related peripheral neuropathy or IR neurologic event;
- Any 2 treatment-related Grade 5 events (excluding CRS and ICANS and peripheral neuropathy/IR neurologic event).

7.2.2. Interim Analysis for Futility

An interim analysis for futility will be performed to assess the safety of elranatamab in terms of CRS rate using a dose regimen with 2 step-up priming doses. It will be conducted after the 30 participants enrolled and treated in Part 1 have either completed Cycle 1 of study intervention or discontinued the study intervention prior to the end of Cycle 1.

The primary endpoint of Grade ≥ 2 CRS rate during Cycle 1 will be evaluated at the interim analysis using a futility boundary based on the predictive probability assuming a Beta (0.7, 1.3) prior. More specifically, the study may stop for futility if the predictive probability of observing 20 or fewer participants with Grade ≥ 2 CRS events in 76 participants at the primary analysis based on the data observed at the interim analysis is less than 10%.

The posterior beta-binomial predictive distribution for the number of participants with Grade ≥ 2 CRS events in the second stage of the study is as follows:

$$\pi(r_2 | IA.r, IA.n) = \binom{n_2}{r_2} \frac{B(r_2 + a + IA.r, b + IA.n - IA.r + n_2 - r_2)}{B(a + IA.r, b + IA.n - IA.r)}$$

where IA.r and IA.n denote the number of participants with Grade ≥ 2 CRS events and number of participants at the interim analysis, r_2 and n_2 denote the number of participants with Grade ≥ 2 CRS events and number of participants from the second stage of the study ($n_2 = 46$), and B denotes the Beta function.

The futility boundary based on the posterior predictive distribution can be obtained using the exact method to calculate the probability of observing 20 or fewer participants with Grade ≥ 2 CRS events in 76 participants at the primary analysis, ie,

$$P(IA.r + r_2 \leq 20 | IA.r, IA.n) = \sum_{r_2=0}^{20-IA.r} \pi(r_2 | IA.r, IA.n)$$

With 30 participants at the interim analysis, if there are 11 or more participants with Grade ≥ 2 CRS events, further accrual may be stopped for the study. Otherwise, the study will proceed as planned to the primary analysis as described in [Section 6.1](#).

The interim analysis may also be performed at other time points for the purpose of safety assessment and/or supporting clinical development. The exact futility boundary will be updated prior to the time of the analysis based on the actual number of participants enrolled and treated. [Table 9](#) summarizes the futility boundary in terms of number of participants with Grade ≥ 2 CRS events at the interim analysis.

Table 9. Futility Boundary (Number of Participants with Grade ≥ 2 CRS Events) at the Interim Analysis

Number of evaluable participants at the interim analysis	15-17	18-21	22-24	25-27	28-31	32-35	36-38	39-42
Maximum # of participants with Grade ≥ 2 CRS events at the interim analysis to stop the study for futility	7	8	9	10	11	12	13	14

Table 10 presents the operating characteristics of a few scenarios if the interim futility analysis is performed based on the first 15 participants in the Safety Analysis Set. For example, if 3 participants had Grade ≥ 2 CRS events in the first 15 participants at the interim analysis, the predictive probability of observing ≤ 20 participants with Grade ≥ 2 CRS events in 76 participants at the primary analysis is 75.2%.

Table 10. Predictive Probability at the Primary Analysis with 15 Participants at the Interim Analysis

Scenario	Number of Grade ≥ 2 CRS Event at the Interim Analysis (N=15)	Predictive Probability [Grade ≥ 2 CRS Events $\leq 26.3\%$ (20/76) at the Primary Analysis]
1	2/15	91.3%
2	3/15	75.2%
3	4/15	51.4%
4	5/15	27.8%
5	6/15	11.6%
6	7/15	3.7%

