#### 4. STUDY DESIGN

##### 4.1. Overall Design

Study C1071009 is a prospective, open-label, multicenter, non-randomized Phase 1/2 study aimed to evaluate the safety (in particular the rate of Grade  $\geq 2$  CRS) of a priming dose regimen of eh-anatamab that involves premedication and 2 step-up priming doses to be administered within the first week of treatment (Part 1 and Part 2). Study C1071009 will include RRMM participants who are refractory to at least 1 PI, 1 IMiD, and 1 anti-CD38 mAb.

All participants enrolled in Part 1 and Part 2 will contribute to the primary objective of the study, ie, assessing the rate of Grade  $\geq 2$  CRS during C1, as the same dosing regimen is administered to all treatment groups during the first cycle.

Overall, at time of protocol amendment 4, Part 1 and Part 2 (Part 2A and Part 2B) were ongoing, and the enrollment is completed in all cohorts. Part 2C will not be explored. The RP2D was determined from Part 2A and is described below.

Twelve participants were enrolled and treated in Part 2A DL1 (116 mg Q2W from C2D1) and 7 were DLT evaluable. There was one DLT event. Eleven participants were enrolled and treated in Part 2A DL2 (152 mg Q2W from C2D1) and 7 were DLT evaluable. There was one DLT event. During the dose level review meeting (DLRM), the 152 mg Q2W dose was selected as the RP2D with a switch to 152 mg Q4W starting in Cycle 7 (for participants with an IMWG response of PR or better persisting for 2 months). In addition, participants in Part 1 dosed with 76 mg Q2W, with an IMWG response of PR or better persisting for 2 months were also permitted to switch to 152 mg Q4W. RP2D is currently investigated in Part 2B with a dosing of 152 mg Q2W or 152 mg Q4W (depending on IMWG response).

CCI  

All study parts are detailed below.

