**Table 11. Futility Boundary (Number of Participants with Grade  $\geq 2$  CRS Events) at the Interim Analysis**

Number of participants at the interim analysis	15-17	18-21	22-24	25-27	28-31	32-35	36-38	39-42
Minimum # of participants with Grade $\geq 2$ CRS events at the interim analysis to stop the study for futility	7	8	9	10	11	12	13	14

The internal core study team will review the interim futility analysis results and document all decisions in the study TMF. The analysis details will be documented and approved in the SAP.

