**Table 12. Operating Characteristics of Bayesian 2-Stage Dual-Criterion Design for Grade  $\geq 2$  CRS rate**

True Grade <math>\geq 2</math> CRS Rate	Prob of Exceeding Futility Boundary at the Interim (R1/N1 <math>\geq 11/30</math>)	Prob of GO Decision at the Primary Analysis* (R/N <math>\leq 20/76</math> and R1/N1 <math>< 11/30</math>)	Prob of No-GO Decision at the Primary Analysis* (R/N <math>> 20/76</math> and R1/N1 <math>< 11/30</math>)
20%	0.026	0.919	0.055
21%	0.036	0.882	0.082
22%	0.048	0.835	0.116
23%	0.064	0.779	0.157
27%	0.161	0.488	0.351
35%	0.492	0.065	0.443

\* The study does not meet futility criteria at the interim analysis and continues to the primary analysis.

CRS = cytokine release syndrome;

R1 = Number of participants with Grade  $\geq 2$  CRS events required at the interim futility analysis to stop the study for futility;

N1 = Number of participants at the interim analysis;

R = Number of participants with Grade  $\geq 2$  CRS events required to meet the dual criteria at the primary analysis;

N = Number of participants at the primary analysis.

At the time of the primary analysis, the critical number of participants with Grade  $\geq 2$  CRS events to be observed will be updated based on the actual number of participants enrolled and treated.

An interim analysis for non-binding futility will be conducted on the 30 participants enrolled and treated in Part 1 of the study. Details are described in Section 9.4.2.

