5.1.2. Decision Rules

5.1.2.1. Primary Endpoint

The study is designed to have an interim analysis for futility and a primary analysis. The interim analysis will be conducted once 30 participants in Part 1 either complete Cycle 1 of study intervention or discontinued the study intervention prior to the end of Cycle 1. The primary analysis will be conducted once all participants have completed Cycle 1 of study intervention or have otherwise discontinued the study intervention.

[Table 2](#) presents the operating characteristics of this 2-stage design, ie, the probability of early trial termination at the interim futility analysis and the probability of observing the critical number of Grade ≥ 2 CRS (ie, ≤ 20 participants with Grade ≥ 2 CRS events in 76 participants) at the primary analysis if the true Grade ≥ 2 CRS rate is 20%, 21%, 22%, 23%, 27% and 35%, respectively. For example, if the true Grade ≥ 2 CRS rate = 22%, the probability of stopping the study due to futility at the interim analysis is 0.048, and the probability of observing ≤ 20 participants with Grade ≥ 2 CRS rate at the primary analysis is 0.835.

Table 2. Operating Characteristics of Bayesian 2-Stage Dual-Criterion Design

True Grade ≥ 2 CRS Rate	Prob of Exceeding Futility Boundary at the Interim ($R1/N1 \geq 11/30$)	Prob of GO Decision at the Primary Analysis* ($R/N \leq 20/76$)	Prob of No-GO Decision at the Primary Analysis ($R/N > 20/76$)
20%	0.026	0.919	0.055
21%	0.036	0.882	0.082
22%	0.048	0.835	0.116
23%	0.064	0.779	0.157
27%	0.161	0.488	0.351
35%	0.492	0.065	0.443

* The study does not meet futility criteria at the interim analysis and continues to the primary analysis.

CRS = cytokine release syndrome;

R1 = Number of participants with Grade ≥ 2 CRS events at the interim futility analysis to stop the study for futility;

N1 = Number of participants at the interim analysis;

R = Number of participants with Grade ≥ 2 CRS events to meet the dual criteria at the primary analysis;

N = Number of participants at the primary analysis.

At the time of the primary analysis, the critical number of participants with Grade ≥ 2 CRS events to be observed will be updated based on the actual number of participants enrolled and treated.

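### Does calling the futility counts in SAP Table 9 a maximum turn the interim stopping rule the wrong way round?

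*SAP*

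**What the plan says.** SAP section 7.2.2 sets the futility rule for the primary endpoint, Grade ≥2 CRS in Cycle 1. With a Beta(0.7, 1.3) prior, the study may stop if the predictive probability of 20 or fewer cases among 76 "at the primary analysis based on the data observed at the interim analysis is less than 10" per cent. The section prints the beta-binomial formula with a second stage of 46, and applies it to the planned look: "With 30 participants at the interim analysis, if there are 11 or more participants with Grade" ≥2 CRS, accrual may stop.

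Table 9 then gives one count for each range of interim sizes: 7 (15–17), 8 (18–21), 9 (22–24), 10 (25–27), 11 (28–31), 12 (32–35), 13 (36–38) and 14 (39–42). The row label is "Maximum # of participants with Grade ≥ 2 CRS events at the interim analysis to stop the study for futility". Protocol Table 11 has the same ranges and counts, but its label starts "Minimum # of participants with Grade".

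Three other statements matter:

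- SAP Table 2 heads its stopping column "Prob of Exceeding Futility Boundary at the Interim" and defines it as R1/N1 ≥ 11/30.
- SAP 7.2.2 adds: "The exact futility boundary will be updated prior to the time of the analysis based on the actual number of participants enrolled and treated".
- Protocol 9.5.1 describes the look as follows: "An interim analysis for non-binding futility will be conducted on the 30 participants enrolled and treated in Part 1 of the study".

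**The concern.** A stopping boundary for an adverse outcome is the smallest count at which one stops. Calling it a maximum either has no sensible meaning or suggests a different rule. Taken literally, few events would be a reason to stop and many would not, which nobody would apply to a toxicity endpoint. The misreading that could really happen is off by one: the printed figure taken as the largest count at which the study may continue, so that it stops at 12 of 30 instead of 11.

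That reading errs towards continuing when CRS is too frequent. Table 9 is also the only list in the SAP of stop counts for interim sizes other than 30, and section 7.2.2 allows looks at other times. If the label were followed, the interim analysis would not have the operating characteristics that the SAP reports.

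**Working it through.** **Inputs (SAP 7.2.2).** Prior a = 0.7, b = 1.3; final size 76; success is a total of at most 20; stop if the predictive probability is below 0.10. With r events among n at the interim, the second stage has n2 = 76 − n.

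**Formula.**

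P(r + r2 ≤ 20 | r, n) = Σ from k = 0 to 20 − r of C(n2, k) · B(k + a + r, b + n − r + n2 − k) / B(a + r, b + n − r)

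**Step 1: reproduce SAP Table 10 (n = 15, n2 = 61).** For 2, 3, 4, 5, 6 and 7 events the formula gives 91.3, 75.2, 51.4, 27.8, 11.6 and 3.7%, exactly as printed. Six events stay above 10% and seven fall below, so 7 is the lowest stopping count at n = 15.

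**Step 2: the planned look (n = 30, n2 = 46).**

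- r = 10: Σ k = 0..10 of C(46, k) · B(k + 10.7, 67.3 − k) / B(10.7, 21.3) = 0.164, continue.
- r = 11: Σ k = 0..9 of C(46, k) · B(k + 11.7, 66.3 − k) / B(11.7, 20.3) = 0.067, stop.
- r = 12: 0.022, stop.

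**Step 3: all 28 interim sizes in Table 9.** The table shows the range of predictive probabilities across the sizes in each column.

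| n | Printed count | One event fewer | Printed count met |
|---|---|---|---|
| 15–17 | 7 | 0.1162–0.2021 | 0.0366–0.0785 |
| 18–21 | 8 | 0.1078–0.2298 | 0.0354–0.0983 |
| 22–24 | 9 | 0.1294–0.2071 | 0.0472–0.0882 |
| 25–27 | 10 | 0.1156–0.1852 | 0.0421–0.0777 |
| 28–31 | 11 | 0.1019–0.2020 | 0.0365–0.0883 |
| 32–35 | 12 | 0.1135–0.2164 | 0.0422–0.0969 |
| 36–38 | 13 | 0.1232–0.1891 | 0.0467–0.0808 |
| 39–42 | 14 | 0.1036–0.1985 | 0.0371–0.0848 |

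Every printed count meets the rule and one event fewer never does. The counts are minima, without exception.

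**Step 4: the off-by-one reading against SAP Table 2.** Let X ~ Bin(30, p) and Y ~ Bin(46, p). For a stopping threshold t, P(stop) = P(X ≥ t) and P(GO) = Σ over x < t of P(X = x) · P(Y ≤ 20 − x).

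| True rate | t = 11: stop / GO | t = 12: stop / GO | Change in GO |
|---|---|---|---|
| 20% | 0.026 / 0.919 | 0.009 / 0.928 | +0.009 |
| 21% | 0.036 / 0.882 | 0.014 / 0.893 | +0.011 |
| 22% | 0.048 / 0.835 | 0.020 / 0.847 | +0.012 |
| 23% | 0.064 / 0.779 | 0.028 / 0.792 | +0.013 |
| 27% | 0.161 / 0.488 | 0.084 / 0.500 | +0.012 |
| 35% | 0.492 / 0.065 | 0.345 / 0.068 | +0.003 |

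The t = 11 column reproduces SAP Table 2 in every row, so the design was evaluated with stopping at 11 or above. The t = 12 reading would cut the stopping probability at a true rate of 35% by 0.492 − 0.345 = 0.147. It would raise the chance of wrongly reaching GO at that rate by only 0.003, because the final criterion of 20 of 76 still has to be met.

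**The case for a change.** The case for acting is that the word is plainly wrong, cannot be explained as a misread character, and sits in the controlled document that analysts work from. The correction is one word. The off-by-one reading is also not far-fetched: the SAP Table 2 heading speaks of exceeding the boundary, which on its own could suggest that 11 does not yet count.

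The first part stands: the label is incorrect, and the protocol has it right. The rest carries little weight. The inequality printed under the Table 2 heading includes 11. The paragraphs that introduce Table 9 state the criterion, the formula and the count at which stopping begins for 30 participants. Table 10, directly below, shows the direction again at 15. Nor can the label be a deliberate change of rule: the SAP's two version tables mention none, and the later Protocol Amendment 4 still prints the minimum. An analyst would compute the boundary from the formula, as the SAP requires for the actual sample size, and would not rely on a row label.

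One similar item is only a possible reading error. In the supplied text, the SAP Table 7 column for 7 events is headed 23-36, overlapping its neighbours, where Protocol Table 9 has 23-26. The stated criterion gives 7 for n = 23 to 26 only. A single digit in a table read from PDF is no basis for a finding.

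**Conclusion.** The label in SAP Table 9 is a clerical slip. All 28 boundary values are correct as minimum stopping counts, and the rule is stated correctly in SAP 7.2.2, SAP Table 2, SAP Table 10 and Protocol Table 11. Correcting the word would change no count, analysis, operating characteristic or conclusion.

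The practical exposure is smaller still. The futility rule is advisory, the boundary was to be recalculated before use, and Part 2 was to open only after about 30 participants had entered Part 1 and the available data had been reviewed. Protocol 4.1 now reports that "the enrollment is completed in all cohorts", so a futility look can no longer stop accrual.

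Had someone nevertheless applied the off-by-one reading at the planned look, the loss would have been a stopping probability of 0.345 instead of 0.492 at a true rate of 35%, and a GO probability higher by at most 0.013 at the rates in SAP Table 2. These figures assume 30 participants at the interim, 76 at the end, and that a crossed boundary leads to stopping. No change to the plan is needed.
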